9.6.8 Exposure to Concomitant Medication

Concomitant medications are defined as medications with start date or end date on or after the date of first dose and start date before the date of the last dose + 30 days or are ongoing at the time of first dose. For the purpose of determining if a medication should be noted as a concomitant medication, the imputation rules stated in [Section 8.3](#) will be used. The number and proportion of subjects receiving concomitant medications will be summarized by preferred name as coded by the World Health Organization Drug (WHO DRUG) dictionary. A subject is counted once if he/she reported one or more medications. The summaries will be ordered by descending frequency of preferred name in the total group.

9.7 Other Analyses

9.7.1 Analyses of Pharmacokinetic or Pharmacokinetic/Pharmacodynamic Endpoints

PK/PDn analyses will be provided by the Department of Clinical Pharmacology, Modeling & Simulation (CPMS). Actual collection times of PK samples will be recorded to assess the plasma concentration. The PK parameter estimates for carfilzomib will be summarized. Exploratory analyses may be performed to evaluate the relationship between the estimated PK parameters and selected safety, biomarker, or clinical effect

endpoints. In addition, the population modeling program may be used to fit a nonlinear mixed effects model to estimate PK parameters. Details regarding the analyses will be provided in a separate analysis plan by CPMS.

9.7.2 Analyses of Minimal Residual Disease Negative Rate Endpoints

The analysis of MRD[-] rate will not be included in the clinical study report (CSR). The MRD analyses will be summarized in a separate analysis plan by **Clinical Biomarkers & Diagnostics** group.

9.7.3 Analyses of Patient Reported Outcomes and Other Health Related Quality of Life Endpoints

Results from the subject convenience and satisfaction questionnaire will be summarized **descriptively** at Cycle 3 Day 1 and Cycle 18 Day 1 **by presenting the number and percentage of subjects for each item of the questionnaire** **The denominator for percentage will be based on (1) the number of subjects in the safety analysis set; (2) the number of subjects received carfilzomib at the specified timepoint (Cycle 3 Day 1, Cycle 18 Day 1).**

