9.2.1.3 Dexamethasone

Dexamethasone will be taken by mouth or by IV infusion once-daily on Days 1 (\pm 2), 8 (\pm 2), and 15 (\pm 2) for all cycles and on Day 22 (\pm 2) of Cycles 1 through 8. Dexamethasone will be administered at least 30 minutes (but no more than 4 hours) prior to carfilzomib. Subjects receiving dexamethasone IV on Days 1, 8, and 15 may receive dexamethasone orally on Day 22.

9.2.2 *CARFILZOMIB AND LENALIDOMIDE DOSE MODIFICATION GUIDELINES*

Dose reduction levels of carfilzomib and lenalidomide for toxicity management of individual subjects are provided in [Table 5](#) and [Table 6](#), respectively:

Table 5 Dose Decrement for Carfilzomib

Nominal Dose (mg/m ²)	Reduced Carfilzomib Doses (mg/m ²)		
	Dose -1	Dose -2	Dose -3
20	Discontinue		
56	45	36	Discontinue
70	56	45	36

Table 6 Dose Decrement for Lenalidomide

Nominal Dose (mg)	Reduced Lenalidomide Doses (mg)		
	Dose -1	Dose -2	Dose -3
25	15	10	5
10	5	Discontinue	—

Treatment guidelines for specific hematologic toxicities are outlined in [Section 9.2.2.1](#) and nonhematologic toxicities in [Section 9.2.2.2](#). In addition to dose reductions, administration of carfilzomib and/or lenalidomide may be held temporarily in the event of a treatment-related toxicity at the investigator's discretion. When administration of carfilzomib and/or lenalidomide is held, the reason must be documented in the case report form (CRF), and the medical monitor must be notified within 2 business days of the scheduled dose ([Section 9.1](#)).

If either the lenalidomide or carfilzomib dose level is reduced during a given cycle, the reduced dose level will be continued for the next cycle. If the reduced dose level is tolerated for a complete cycle, the subject may, at the investigator's discretion, resume the dose level prior to the reduction at the start of the subsequent cycle.

Carfilzomib or lenalidomide can be discontinued in the event of a treatment-related toxicity that, in the opinion of the investigator, warrants discontinuation. The subject will be considered still on protocol treatment as long as carfilzomib is being administered.

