10.1.9 SUBJECT CONVENIENCE AND SATISFACTION

Subject convenience and satisfaction will be assessed in all subjects by questionnaire at Cycle 3 Day 1 and Cycle 18 Day 1 (see [Appendix D](#)). The questionnaire should be administered prior to treatment with carfilzomib.

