6.1 Safety Analysis Set

The safety analysis set includes all subjects who received at least one dose of study drug.

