8.3 Handling of Missing and Incomplete Data

Missing and incomplete data will be identified through programmatic checks and a review of the tables and listings created within Biostatistics. Missing and incomplete data will be identified for investigation, and possible resolution, by DM and Global Study Management prior to each planned data snapshot and final database lock.

The handling of dropouts and missing disease status assessments for the efficacy variables is described in the description of the analyses. In general, data will be analyzed as retrieved from the study database and no imputation for missing data will be performed. Exceptions to this rule are detailed as below.

Missing or incomplete dates for adverse events, concomitant medications will be imputed as outlined by the algorithms below.

Table 3. Imputation Rules for Partial or Missing Start Dates

Start Date		Stop Date						
		Complete: yyyyymmdd		Partial: yyyyymm		Partial: yyyy		Missing
		< 1 st dose	≥ 1 st dose	< 1 st dose yyyymm	≥ 1 st dose yyyymm	< 1 st dose yyyy	≥ 1 st dose yyyy	
Partial: yyyymm	= 1 st dose yyyymm	2	1	2	1	n/a	1	1
	≠ 1 st dose yyyymm		2		2	2	2	2
Partial: yyyy	= 1 st dose yyyy	3	1	3	1	n/a	1	1
	≠ 1 st dose yyyy		3		3	3	3	3
Missing		4	1	4	1	4	1	1

1 = Impute the date of first dose

2 = Impute the first of the month

3 = Impute January 1st of the year

4 = Impute January 1st of the stop year

Note: If the start date imputation leads to a start date that is after the stop date, then do not impute the start date.

Imputation Rules for Partial or Missing Stop Dates

1. Initial imputation
 - If the month and year are present, impute the last day of that month
 - If only the year is present, impute December 31 of that year
 - If the stop date is entirely missing, assume the event or medication is ongoing
2. If the stop date imputation leads to a stop date that is after the death date, then impute the stop date as the death date.
3. If the stop date imputation leads to a stop date that is before the start date, then there is a data error and do not impute the stop date. (ie, set the stop date as missing).

If a partial or complete stop date is present and the 'ongoing' or 'continuing' box is checked, then it will be assumed that the adverse event or concomitant medication is ongoing. Missing stop dates will not be imputed beyond the subject last contact date or data cutoff date.

Imputation Rules for Partial or Missing Death Dates:

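### SAP 9.7.3 never divides questionnaire counts by the subjects who answered, so every response percentage is diluted by missing forms and, on the safety set, by treatment discontinuation

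*SAP*

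**What the plan says.** SAP 9.7.3 summarizes the questionnaire at Cycle 3 Day 1 and Cycle 18 Day 1 "by presenting the number and percentage of subjects for each item of the questionnaire". It fixes two denominators: (1) the safety analysis set and (2) "the number of subjects received carfilzomib at the specified timepoint". The SAP's summary of changes shows that Amendment 1 added this denominator text, so it is a deliberate rule.

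The surrounding provisions are:

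- Protocol 10.1.9 on who is asked and when: "Subject convenience and satisfaction will be assessed in all subjects by questionnaire at Cycle 3 Day 1 and Cycle 18 Day 1".
- Protocol 10.1.9 on the order: "The questionnaire should be administered prior to treatment with carfilzomib".
- Protocol 9.2.2 on held doses: "administration of carfilzomib and/or lenalidomide may be held temporarily in the event of a treatment-related toxicity".
- SAP 6.1: "The safety analysis set includes all subjects who received at least one dose of study drug". The set therefore keeps subjects who left treatment before the questionnaire visit.
- SAP 8.3: in general "no imputation for missing data will be performed". The listed exceptions are rules for dates.
- Protocol 13.5.4 asks only for a descriptive summary and names no denominator.

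SAP 9.7.3 mentions no respondent denominator, completion rate or missing category. It also does not say whether the numerator of the second percentage is limited to subjects dosed that day.

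**The concern.** A reader of the results table will take the percentage beside a response as the share of subjects holding that view. Under SAP 9.7.3 it mixes three things: what respondents thought, how many forms came back and, on the safety set, how many subjects were still on treatment. Two dose groups with the same opinions but different form return would show different percentages. A fall between Cycle 3 and Cycle 18 on the safety set could be attrition alone.

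The SAP does provide for absent data elsewhere. Best response has a not-evaluable category (9.5.1), and cytogenetic risk and staging have an unknown category (9.4.3). The questionnaire has neither.

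A second, smaller matter is that the form precedes dosing while the second denominator is defined by dosing. The people counted above the line need not all be among those below it.

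At stake is a listed exploratory objective (Protocol 4.3). Expected convenience is also part of the study rationale (Protocol 3.5).

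**Working it through.** The documents give no questionnaire percentage, completion rate or expected number of forms, so there is no figure to reproduce. The only input from the documents is the Arm 3 size, N = 33 (SAP 9.1). **All counts of subjects dosed, answering or satisfied are assumptions for illustration.**

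**Step 1: dilution.** Let N be the safety set, D the subjects dosed that day, R the subjects who answered and x those choosing a category.

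- Share of respondents = x/R.
- Second SAP percentage = x/D = (x/R) × (R/D).
- First SAP percentage = x/N = (x/R) × (R/N).

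With N = 33, D = 30, R = 25 and x = 20:

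- Respondents: 20/25 = 80.0%.
- Dosed that day: 20/30 = 66.7%.
- Safety set: 20/33 = 60.6%.

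The other five respondents are 5/25 = 20.0%, 5/30 = 16.7% and 5/33 = 15.2%. On the dosed denominator the two groups sum to 25/30 = 83.3%. The remaining 16.7% is blank and has no planned row.

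**Step 2: range.** N = 33 and D = 30, with about 80% of respondents satisfied:

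| Answered | Satisfied | % of answered | % of dosed | % of safety set |
|---|---|---|---|---|
| 30 | 24 | 80.0 | 80.0 | 72.7 |
| 27 | 22 | 81.5 | 73.3 | 66.7 |
| 25 | 20 | 80.0 | 66.7 | 60.6 |
| 21 | 17 | 81.0 | 56.7 | 51.5 |
| 15 | 12 | 80.0 | 40.0 | 36.4 |

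Opinion barely moves down the table; only form return does. With full return among dosed subjects, the second SAP percentage equals the respondent share.

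**Step 3: attrition on the safety set.** Assume full form return at both visits and 80% satisfied at both, with 30 dosed at Cycle 3 and 20 at Cycle 18. The safety-set figure is 24/33 = 72.7% and then 16/33 = 48.5%. That is a fall of 8/33 = 24.2 points with no change in opinion and no missing form. The dosed denominator stays at 24/30 = 16/20 = 80.0%.

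**Step 4: numerator and second denominator.** Let r_d be respondents who were dosed and r_u respondents whose carfilzomib was held that day. If each item takes one answer and the numerator is not restricted, the categories sum to (r_d + r_u)/D. This passes 100% only when r_u > D − r_d, that is, when undosed respondents outnumber dosed non-respondents.

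- D = 30, r_d = 27, r_u = 2: 29/30 = 96.7%.
- D = 30, r_d = 30, r_u = 2: 32/30 = 106.7%. A single category passes 100% here only if nearly everyone chooses it; at 90% it is 0.9 × 32/30 = 96.0%.

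This cannot happen on the safety set, because respondents are a subset of it.

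**The case against.** The strongest defence is that both denominators are reasonable. The first follows the SAP-wide default in 9.1. The second removes most subjects who are already off treatment, and showing both lets a reader separate attrition from results among treated subjects. A respondent-only percentage has its own weakness: at Cycle 18 it describes those who stayed on treatment and returned a form, and may look favourable for that reason. SAP 9.7.3 also presents counts, so if each item takes one answer a reader can add the categories and recover the respondent share. If nearly all dosed subjects complete the form, the second percentage is close to that share anyway.

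Most of this stands as a reason to keep the two denominators. It does not justify leaving out the respondent percentage and completion line. Neither planned denominator separates missing forms from answers, and recovering the share by hand depends on the form's structure. The questionnaire items (Protocol Appendix D) are not in the available text, so single-choice items cannot be confirmed.

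On the numerator, it is fair to say that a percentage of dosed subjects would ordinarily count answers among dosed subjects only. The mismatch also needs the visit to go ahead as Day 1 with carfilzomib withheld, rather than the cycle being delayed. The documents permit that situation, and the SAP does not state the restriction.

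**Conclusion.** The point holds as a minor one. SAP 9.7.3 plans no percentage of those who answered, so every response category is understated by the factor answered/denominator. On the safety set, discontinuation adds to this, most of all at Cycle 18. In the assumed Arm 3 example, 80% becomes 67% or 61%; the actual size depends on completion and retention, which the documents do not give. Denominator (2) need not contain its numerator as written.

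Two stronger readings are tempting and are not supported:

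- A reader might infer that non-response is counted as dissatisfaction. Nothing scores a blank that way, and SAP 8.3 imputes only dates. Blanks shrink satisfied and dissatisfied shares by the same factor; only someone who subtracts the satisfied share from 100% would be misled.
- A reader might infer that percentages will exceed 100%. That is an edge case, confined to the second denominator and to the condition in step 4, and it disappears if the numerator is limited to dosed subjects.

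The endpoint is exploratory and summarized descriptively, and SAP 2.2 plans no formal hypothesis test. No primary or secondary endpoint is affected.

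**What to change.** Amend SAP 9.7.3 as follows:

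- Add item percentages based on the subjects who answered that item at that visit.
- For each visit and dose group, report the number expected, the number completed and the completion rate.
- If the two planned denominators are kept, show a missing row under each so that the blank share is visible.
- For the second denominator, either count only answers from subjects dosed at that visit, or redefine it as subjects on treatment and due the questionnaire.

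The cost is a few sentences in the SAP and some extra table rows. No new data collection is needed.

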Appendix A. Dose Intensity Calculations

Dose intensity is calculated for each drug component and expressed as an average dose per unit of time. In this study, we choose the time unit to be week.

1. The formula for Actual Dose Intensity (mg/m²/wk or mg/wk) is defined as:

$$\text{Actual Dose Intensity (mg/m}^2\text{/wk or mg/wk)} = \frac{\text{Cumulative actual dose (mg or mg/m}^2\text{)}}{\text{Duration of exposure (wk)}}$$

- Cumulative actual dose (mg or mg/m²) received of carfilzomib and dexamethasone is defined as the cumulative dose of carfilzomib/dexamethasone, respectively, a subject received during the treatment period of the study.
- Duration of exposure (weeks) is defined as
$$\frac{(\text{last dose date} - \text{first dose date}) + \text{planned interval to next treatment week}}{7 \text{ days}}$$

Carfilzomib dosing schedule and planned interval

Cycle	Cycle Day of Treatment	Dose (mg/m ²)	Interval (Days) to Next Planned Treatment Week (or Completion)
1	Day 1	20	7
	Day 8	56 if Cohort 1; Cohort 4; Arm 3 70 if Cohort 2; Arm 1; Arm 2	7
	Day 15	56 if Cohort 1; Cohort 4; Arm 3 70 if Cohort 2; Arm 1; Arm 2	14
2 -18	Day 1	56 if Cohort 1; Arm 3 70 if Cohort 2; Cohort 4; Arm 1; Arm 2	7
	Day 8	56 if Cohort 1; Arm 3 70 if Cohort 2; Cohort 4; Arm 1; Arm 2	7
	Day 15	56 if Cohort 1; Arm 3 70 if Cohort 2; Cohort 4; Arm 1; Arm 2	14

Dexamethasone dosing schedule and planned interval

Cycle	Cycle Day of Treatment	Dose (mg)	Interval (Days) to Next Planned Treatment
1 - 8	Day 1	40	7
	Day 8	40	7
	Day 15	40	7
	Day 22	40	7
9 -18	Day 1	40	7
	Day 8	40	7
	Day 15	40	14

Lenalidomide dosing schedule and planned interval

Cycle	Cycle Day of Treatment	Dose (mg)	Interval (Days) to Next Planned Treatment
1 - 18	Day 1 - 7	25	7
	Day 8 – 14	25	7
	Day 15 - 21	25	7

2. The formula for Planned Dose Intensity (mg/m²/wk or mg/wk) is defined as:

$$\text{Planned Dose Intensity (mg/m}^2\text{/wk or mg/wk)} = \frac{\text{Cumulative planned dose (mg/m}^2\text{ or mg)}}{\text{Number of protocol specified treatment weeks}}$$

- Number of protocol specified treatment weeks is the sum of treatment weeks the patient completed. It is counted by 4 weeks for a completed or skipped cycle. For the last cycle, use the following rules to count:

Carfilzomib

1 week if the last dose is on Day 1;
2 weeks if the last dose is on Day 8;
4 weeks if the last dose is on Day 15;

Example: Patient's last carfilzomib is on cycle 2 Day 8. The number of protocol specified treatment weeks is D=4x1+2=6 weeks.

Dexamethasone

1 week if the last dose is on Day 1;
2 weeks if the last dose is on Day 8;
3 weeks if the last dose is on Day 15 in Cycle 1 to 8;
4 weeks if the last dose is on Day 15 after Cycle 8 or Day 22;

Lenalidomide

1 week if the last dose is on Day 1-7;
2 weeks if the last dose is on Day 8-14;
4 weeks if the last dose is on Day 15- 21;

- Cumulative planned dose for each drug is the sum of protocol specified doses across the treatment weeks as determined above. Per study treatment regimen on protocol:

Carfilzomib cumulative planned dose:

For Cohort 1; Arm 3: [20, 56, 56, 0], [56, 56, 56, 0]

For Cohort 2, Arm 1; Arm 2: [20, 70, 70, 70], [70, 70, 70, 0]

For Cohort 4: [20, 56, 56, 0], [70, 70, 70, 0]

Dexamethasone cumulative planned dose:

[40, 40, 40, 40], repeated 7 more times, [40, 40, 40, 0]

Lenalidomide cumulative planned dose:

[25, 25, 25, 25, 25, 25, 25], [25, 25, 25, 25, 25, 25], [25, 25, 25, 25, 25, 25, 25],
[0, 0, 0, 0, 0, 0, 0],

3. Relative dose intensity is calculated as actual dose intensity / planned dose intensity
and expressed as a percent.

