5 STUDY DESIGN

This is an open-label, multicenter, Phase 1b, dose-finding study of carfilzomib administered once-weekly in combination with lenalidomide and dexamethasone (KRd) in 28-day cycles to subjects with multiple myeloma.

Subjects may continue to receive study treatment for up to 18 cycles or until 1 or more of the following events occurs:

- Disease progression
- Allogeneic stem cell transplant
- Withdrawal from the study for any reason
- Study termination by the sponsor
- Death

Disease assessments will be conducted at Screening (within 21 days before dosing on Cycle 1 Day 1) and then on Day 1, \pm 3 days, of every cycle beginning with Cycle 2.

Response will be evaluated using the International Myeloma Working Group (IMWG) - Uniform Response Criteria (URC; [Rajkumar, 2011](#); [Appendix C](#)).

NDMM subjects may interrupt study treatment to proceed to hematopoietic stem cell collection, or stem cell collection and ASCT. The investigator will communicate transplant plans with the clinical study team. Upon completion of collection, subjects may resume study treatment (for up to the total of 18 cycles). Study treatment interruption for autologous hematopoietic stem cell collection may not exceed 42 days. Subjects with interruptions longer than 42 days may resume therapy on trial only with the written permission of the

sponsor study medical monitor. Subjects may interrupt study treatment and proceed to ASCT at any time after Cycle 4. Subjects who undergo ASCT may resume study treatment at any time up to posttransplant day 100, as elected by the investigator.

There will be 2 parts in the study.

The first part is the Dose-evaluation Component during which carfilzomib combination regimens will be evaluated ([Table 2](#) and [Figure 1](#)). Approximately 8 dose-limiting toxicity evaluable subjects will be enrolled into each opened Dose-evaluation cohort. Before opening Dose-expansion **arms**, it must be determined that there are not more than 2 dose-limiting toxicities in 8 DLT-evaluable subjects at the dose selected for Dose-expansion.

Dose-expansion **arms** may open once all safety data for at least 1 cycle at maximal dose carfilzomib is reviewed by the CSRC.

[figure not shown]
The second part is the Dose-expansion Component.

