5.7 ESTIMATED STUDY DURATION AND STUDY CLOSURE

The total study duration is expected to be a minimum of 60 months. Approximately 6 months will be required to enroll subjects in the RRMM Dose-evaluation Component of the study. Approximately 9 months will be required to enroll subjects in the RRMM Dose-expansion Component of the study. Subjects will be followed for up to 17 months in order to complete primary safety and efficacy evaluations with up to an additional 12 months of Active Follow-up.

It will take up to approximately **12** months to enroll NDMM subjects into Dose-evaluation Cohort 4, review the safety data, and enroll NDMM subjects into the NDMM Dose-expansion **Arm 3**. Subjects will be followed for up to 17 months on treatment (with an allowed interruption of up to 4.5 months for ASCT), and for 12 months for Active Follow up.

Based on these assumptions, it is estimated that the final analysis will occur approximately 60 months after the first subject is enrolled.

The end of study will occur when the last subject leaves Active Follow-up.

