9.6.7 Exposure to Investigational Product

Extent of exposure to all study treatments (carfilzomib, lenalidomide, and dexamethasone) will be summarized for Safety population

- Duration of treatment (weeks) (carfilzomib in combination with lenalidomide and dexamethasone and each component)
 - Defined as the duration (in weeks) from the date of the first dose of any study drug to the date of the last dose of all study drugs + 1
 - Duration of treatment with carfilzomib / lenalidomide / dexamethasone is defined as duration (in weeks) from the date of the first dose of carfilzomib / lenalidomide / dexamethasone to the date of the last dose of carfilzomib / lenalidomide / dexamethasone + 1
- Total number of treatment cycles received (carfilzomib in combination with lenalidomide and dexamethasone and each component)
 - Defined as the total number of treatment cycles in which at least one dose of any study drug is administered.
 - Number of cycles with carfilzomib / lenalidomide / dexamethasone is defined as the total number of treatment cycles in which at least one dose of carfilzomib / lenalidomide / dexamethasone is administered.
- **Number of treatment cycles received (carfilzomib in combination with lenalidomide and dexamethasone and each component) prior to stem cell transplant (SCT) for subjects who had SCT.**

- **Number of treatment cycles received (carfilzomib in combination with lenalidomide and dexamethasone and each component) for subjects who did not have SCT.**
- Number (%) of subjects dosed by cycle (carfilzomib in combination with lenalidomide and dexamethasone and each component)
- Number of doses of carfilzomib / lenalidomide /dexamethasone administered
 - Defined as the total number of non-zero doses of carfilzomib / lenalidomide /dexamethasone respectively, a subject received during the treatment period of the study.
- Cumulative dose received of carfilzomib (mg and mg/m²), lenalidomide (mg) / dexamethasone (mg) across all cycles, defined as the cumulative dose of carfilzomib / lenalidomide / dexamethasone, respectively.
- Average dose of carfilzomib (mg and mg/m²), lenalidomide (mg), and dexamethasone (mg) per administration, defined as the total dose received divided by the number of doses administered
- Relative dose intensity of carfilzomib / lenalidomide / dexamethasone, calculated as the ratio of actual dose intensity to planned dose intensity and expressed as a percent ([Appendix A](#)).

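### SAP Appendix A counts a protocol-permitted transplant or stem-cell-collection pause as exposure time, so a fully dosed NDMM subject who resumes KRd scores a relative dose intensity well below 100%

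*SAP*

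**What the plan says.** **The permitted pause.** Protocol section 5 lets NDMM subjects interrupt treatment for stem-cell collection, for up to 42 days (longer only with the medical monitor's written permission), or for ASCT after Cycle 4. On resumption it says: "Subjects who undergo ASCT may resume study treatment at any time up to posttransplant day 100, as elected by the investigator". Treatment can then continue to a total of 18 cycles. Protocol section 5.7 builds the timeline "with an allowed interruption of up to 4.5 months for ASCT", and SAP section 7.3 repeats that allowance.

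**Actual dose intensity (SAP Appendix A).** Cumulative actual dose is divided by duration of exposure. That duration is last dose date minus first dose date, plus the "planned interval to next treatment week", all over 7 days. Nothing is subtracted for a pause.

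**Planned dose intensity (SAP Appendix A).** The denominator is defined thus: "Number of protocol specified treatment weeks is the sum of treatment weeks the patient completed". The counting rule is: "It is counted by 4 weeks for a completed or skipped cycle". The numerator follows the same weeks: "Cumulative planned dose for each drug is the sum of protocol specified doses across the treatment weeks as determined above".

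**Duration of treatment (SAP section 9.6.7).** It runs "from the date of the first dose of any study drug to the date of the last dose of all study drugs + 1". The only exposure outputs specific to transplant are cycle counts: cycles before transplant in those who had one, and cycles in those who did not.

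**The concern.** RDI compares dose received per week with dose planned per week, and the two sides use different clocks. The actual side runs on the calendar and keeps ticking through a transplant. The planned side runs on treatment weeks and does not recognise the pause as time with no planned dose.

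Extent and duration of exposure is part of the primary safety and tolerability endpoint (Protocol 13.1.1, SAP 2.1), and RDI is one of the summaries in SAP 9.6.7 that describe it. A low RDI is ordinarily read as reductions, delays or omissions for toxicity. Here it could arise in a subject who took every dose and had a transplant that the protocol allows. SAP 9.1 tabulates Arm 1, Cohort 4, their pool and Arm 3 side by side, so differing transplant use could look like differing tolerability.

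**Working it through.** **1. Inputs**
- Collection pause: at most 42 days (Protocol 5).
- ASCT pause: up to 4.5 months (Protocol 5.7). At 30.4 days per month, the SAP 9.5.2 convention, this is 136.8 days = 19.54 weeks.
- A 100-day pause as a shorter case, borrowed from the post-transplant resumption limit (Protocol 5).
- Total cycles: 5 to 18. ASCT comes after Cycle 4, so a resumer has at least 5.
- Arm 3 planned carfilzomib (Appendix A): 20 + 56 + 56 = 132 mg/m² in Cycle 1, then 168 mg/m² per cycle.
- Assumptions: no dose missed or reduced; the pause falls between complete cycles.

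**2. The SAP's own example.** With the last carfilzomib dose on Cycle 2 Day 8, planned weeks are 4 × 1 + 2 = 6, as stated. Duration of exposure is (35 + 7)/7 = 6 weeks. The clocks agree and a fully dosed Arm 3 subject scores 100%, so the method scores full dosing without a pause as 100%.

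**3. Adding a pause.** Actual and planned cumulative dose cancel for a fully dosed subject. With C cycles and a gap of G days,

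RDI = 4C / (4C + G/7).

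| Gap | 5 cycles | 8 cycles | 12 cycles | 18 cycles |
|---|---|---|---|---|
| 42 days (6.0 wk) | 20/26.0 = 76.9% | 32/38.0 = 84.2% | 48/54.0 = 88.9% | 72/78.0 = 92.3% |
| 100 days (14.29 wk) | 20/34.29 = 58.3% | 32/46.29 = 69.1% | 48/62.29 = 77.1% | 72/86.29 = 83.4% |
| 4.5 months (19.54 wk) | 20/39.54 = 50.6% | 32/51.54 = 62.1% | 48/67.54 = 71.1% | 72/91.54 = 78.7% |

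Cohort 4 carfilzomib gives the same figures. If the 4.5 months is measured dose to dose, so that it contains the 14 days already planned after Day 15, the last row becomes 53.3%, 64.6%, 73.2% and 80.4%.

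**4. Counting the gap as skipped cycles.** Take 4.5 months as 5 skipped cycles.
- 8 cycles, full planned dose in the skipped cycles: planned (132 + 12 × 168)/52 = 41.31 mg/m²/wk; actual (132 + 7 × 168)/51.54 = 25.38; RDI 61.4%.
- 18 cycles, full planned dose: planned (132 + 22 × 168)/92 = 41.61; actual (132 + 17 × 168)/91.54 = 32.64; RDI 78.4%.
- Zero planned dose in the skipped cycles: 25.38/(1308/52) = 100.9% at 8 cycles and 32.64/(2988/92) = 100.5% at 18.

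Only the zero-dose version repairs the ratio, and the SAP contains no such rule.

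**5. Durations after 18 cycles with the 4.5-month gap**
- Appendix A carfilzomib exposure: (490 + 14)/7 = 72 weeks without the gap; (504 + 136.8)/7 = 91.5 weeks with it.
- Section 9.6.7 duration, last dose being lenalidomide on Cycle 18 Day 21 and the + 1 read as one day: (496 + 1)/7 = 71 weeks without; (497 + 136.8)/7 = 90.5 weeks with.

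**6. After removing the gap.** Carfilzomib in Arm 3 and Cohort 4, and dexamethasone, return to 100%. Lenalidomide gives about 100.2-100.4%, because a last dose on Day 21 plus 7 days closes the final cycle at 27 days. Arm 1 does not return to 100%. Appendix A lists its Cycle 1 planned vector as [20, 70, 70, 70], while the schedule table in the same appendix has three Cycle 1 doses. A subject dosed to that table scores (160 + 7 × 210)/(230 + 7 × 210) = 1630/1700 = 95.9% at 8 cycles and 3730/3800 = 98.2% at 18.

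**The case against.** **The skipped-cycle rule may already cover it.** Planned dose sums protocol doses, and the schedule table stops at Cycle 18. If 5 skipped cycles are added to 18 given, the extra cycles have no listed dose, and RDI returns to about 100.5%. That reading is possible, but it helps only when given plus skipped cycles run past 18. At 8 cycles plus 5 skipped, all 13 lie inside the schedule, planned dose accrues in each, and RDI is about 61%. The SAP also does not say that a transplant pause is a skipped cycle.

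**First-to-last-dose duration is a legitimate measure.** This stands. A reader might infer that the 9.6.7 duration is wrong. It is openly defined and valid as elapsed time; it is just not time on drug, and the interruption length is not reported beside it.

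**Other outputs are not distorted.** This also stands. Cycles received, number of doses, cumulative dose and average dose per administration do not depend on the gap. SAP 9.2 counts collections and transplants, and 9.6.7 counts subjects with delays and interruptions. A careful reader could suspect the cause of a low RDI, but could not recover the size of the effect from these tables.

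**The stakes are modest.** No hypothesis test is planned (SAP 2.2), RRMM and NDMM are presented separately (SAP 9.1), and the primary endpoint does not name RDI. A reader might infer that a planned RRMM versus NDMM comparison is biased; the documents plan none.

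**Conclusion.** The Appendix A rule, applied as written, gives a misleading RDI for any NDMM subject who resumes after a permitted pause. For a fully dosed subject with 5 to 18 total cycles (carfilzomib, Arm 3 or Cohort 4) it is about 51-79% after a 4.5-month ASCT gap, 58-83% after 100 days and 77-92% after a 42-day collection gap, against 100% without a pause. These figures assume full dosing and a pause between complete cycles.

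Three stronger readings are not supported. A single range such as 60-80% for every pause would be wrong: it fits only a near-maximum ASCT gap with about 8 to 18 cycles. Subtracting the gap does not restore 100% in every arm, because Arm 1 has the separate planned-vector conflict. Nor can one say how far any arm summary moves: SAP Table 1 gives 9 + 9 + 33 = 51 NDMM subjects, but not how many resumed or after how long.

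This should be corrected because RDI would otherwise be read as tolerability. It is not critical, since every affected output is descriptive.

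**What to change.** **Appendix A.** Subtract protocol-permitted collection or ASCT interruption days from duration of exposure, counted from the end of the last planned interval before the pause to the first resumed dose. State that such gaps are not skipped cycles. Alternatively, compute RDI separately before and after transplant.

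**Section 9.6.7.** Keep the elapsed first-to-last-dose duration, add a duration that excludes these interruptions, and report interruption length.

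**Planned vector.** The Cohort 2, Arm 1 and Arm 2 vector [20, 70, 70, 70] and the dosing schedule in the same appendix must be reconciled. Until then a fully dosed Arm 1 subject scores about 96-98% (8 to 18 cycles) even with the gap removed.

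**Cost.** A few sentences of SAP text and a small programming change. Dosing dates bound each pause. The SAP already plans cycle counts before transplant, so transplant pauses should be locatable, but the documents do not show which collection and transplant dates the eCRF holds, and this needs checking. One downside: subtraction also removes any toxicity delay that overlaps the transplant period, so the unadjusted RDI should be kept as a footnote.
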